## Version history

**Table 1 SAP Version History Summary**

SAP Version	Document Date	Protocol Version (Date) on which SAP is based	Change	Rationale
SAP	03-FEB-2021	Protocol Amendment 1 (08-OCT-2020)	Not Applicable	Original version
SAP Amendment 1	31 Mar 2023	Protocol Amendment 3 (21-JUL-2022)	
SAP document updated to change the primary analysis method to be a difference in means and clarify further intercurrent events
 
Analysis of Time to 'Need for Surgery' changed to 'Need for Surgery' at Week 52.
 
Other administrative
	
Protocol Amendment 3 included a change in approach to analysis for primary and secondary endpoint requiring amendment to SAP.. Protocol Amendment 3 included newly defined Intercurrent event of 2 or more missed consecutive doses and clarified COVID-19 related intercurrent events requiring update to SAP.
 
Participants enter the trial with severe NP symptoms.

SAP Version	Document Date	Protocol Version (Date) on which SAP is based	Change	Rationale
			
updates have also been made within this Amendment, including:
 

- Change of reference from PSAP

- COVID-19 SMQ has been removed

	

- Detail of all Adverse Events of Special Interest (AESI) and lab ranges of Potential Clinical Importance (PCI) are now detailed in the OPS.

- COVID-19 SMQ is not required within the reporting of the study.

## 1. INTRODUCTION

The aim of Study 209692 is to assess the efficacy and safety of mepolizumab on top of standard of care (SoC) therapy in the treatment of chronic rhinosinusitis with nasal polyps (CRSwNP) / eosinophilic chronic rhinosinusitis (ECRS) for the purpose of registration in Japan and China.

The purpose of this SAP is to describe the planned analyses to be included in the Clinical Study Report (CSR) for Study 209692. Details of the planned final analyses are provided.

Descriptive study population analyses such as summary of demography and baseline characteristics and additional detail with regards to data handling conventions and the specification of data displays will be provided in the Output and Programming Specification (OPS) document.

### 1.1. Objectives, Estimands and Endpoints

[figure not shown]
#### 1.1.1. Objectives and Endpoints

Objectives	Endpoints
Primary	

 
To evaluate the efficacy of mepolizumab 100mg SC compared to placebo at Week 52 in patients with a diagnosis of CRSwNP / ECRS
 
	
The primary estimands are defined as follows:
 
Treatment Comparison: Mepolizumab 100 mg SC compared to placebo
 
Population: entire trial population of patients with a diagnosis of CRSwNP / ECRS randomised and receiving study treatment
 
Co-primary variables:
 
 
Change from baseline in total endoscopic NP score at Week 52
 
Change from baseline in mean nasal obstruction VAS score during the 4 weeks prior to Week 52
 
 
Summary measure: Difference in mean scores between mepolizumab and placebo
 
Main Intercurrent events (ICE) anticipated:
 
 
Premature discontinuation of study treatment unrelated to the COVID-19 pandemic – to be handled using a treatment policy strategy
 
Changes in background medication or start of a prohibited medication unrelated to the COVID-19 pandemic (e.g. start INCS therapy where absent at
 

Objectives	Endpoints
	
baseline) – to be handled using a treatment policy strategy
 
c) Premature discontinuation of study treatment, change in background medication or start of prohibited medication related to the COVID-19 pandemic – to be handled using a hypothetical strategy
 
d) Surgery, which includes any procedure involving instruments resulting in incision and removal of tissue from the nasal cavity (e.g. polypectomy/functional endoscopic sinus surgery [FESS]) – to be handled using a composite strategy by incorporating occurrence of the event into the definition of the endpoint. Specifically, participants who undergo surgery will be assigned the worst possible score for the endpoint from the day after surgery onwards for inclusion in the analysis
 
e) Course of systemic CS for CRSwNP / ECRS – to be handled using a treatment policy strategy
 
f) Interruption to investigational product of 2 or more consecutive doses – to be handled using a treatment policy

Secondary	

 
To evaluate the impact on quality of life of 100mg mepolizumab compared to placebo at Week 52 in patients with a diagnosis of CRSwNP / ECRS
 
	
 
Change from baseline in Sino-Nasal Outcomes Test-22 (SNOT-22) total score at Week 52
 

 
To evaluate the efficacy of 100mg mepolizumab compared to placebo at Week 52 in terms of mean overall VAS symptom score, mean composite VAS score, Lund Mackay CT score, mean individual VAS symptom score for loss of smell and impact on time to first nasal surgery or course of systemic CS in patients
 
	
 
Change from baseline in mean overall VAS symptom score during the 4 weeks prior to Week 52
 
Change from baseline in the mean composite VAS score (combining VAS scores for nasal obstruction, nasal discharge, mucus in the throat and loss of smell) during the 4 weeks prior to Week 52
 
Change from baseline in Lund Mackay CT score at Week 52
 
Change from baseline in mean individual VAS symptom score for loss of smell during the 4 weeks prior to Week 52
 
Time to first nasal surgery or course of systemic CS for CRSwNP / ECRS up to Week 52
 

Objectives	Endpoints
with a diagnosis of CRSwNP / ECRS	
Other	

CCI

**CONFIDENTIAL**

Objectives	Endpoints
CCI	

Objectives	Endpoints
CC1	
Safety 
 
• To evaluate the safety and immunogenicity of 100mg mepolizumab compared placebo in patients with a diagnosis of CRSwNP / ECRS
 
	
 
• Frequency of Adverse events (AEs)/ Serious adverse events (SAEs) including systemic reactions and local injection site reactions reported
 
• Vital signs (pulse rate, systolic and diastolic blood pressure)
 
• Haematological and clinical chemistry parameters
 
• 12 lead ECG derived endpoints
 
• Presence of anti-mepolizumab antibodies and neutralising antibodies
 

Pharmacokinetics and pharmacodynamics 
 
• To evaluate the pharmacokinetics and pharmacodynamics of 100mg mepolizumab in a subgroup of participants from Japan and China with a diagnosis of CRSwNP / ECRS
 
	
 
• Plasma concentration of mepolizumab
 
• PK/PD (blood eosinophil count) analysis
 

[figure not shown]
### **1.1.2. Estimands**

The primary estimands are the difference between mepolizumab 100mg SC and placebo in a) mean change from baseline in total endoscopic NP score to Week 52 and b) mean change from baseline in mean nasal obstruction VAS score during the 4 weeks prior to Week 52 in participants with a diagnosis of CRSwNP / ECRS, regardless of IP discontinuation or changes in background medication/starting a prohibited medication unrelated to the COVID-19 pandemic, use of systemic CS for CRSwNP / ECRS or interruption of 2 or more consecutive doses of IP, with participants experiencing surgery being assigned the worst possible score from the day after surgery onwards.

Secondary estimands for SNOT-22, VAS scores and Lund Mackay CT score will use the same population, summary measure and strategies for intercurrent events as for the primary estimands. Time to first nasal surgery or course of systemic CS for CRSwNP / ECRS up to Week 52 will be summarised by the hazard ratio between mepolizumab and placebo. The same population and strategies for intercurrent events of treatment discontinuation, changes in background medication/starting a prohibited medication, interruptions of 2 or more consecutive doses of IP and COVID-19 pandemic related intercurrent events will be used as for the primary estimands. Surgery or a course of systemic CS for CRSwNP / ECRS will both be considered events within the analysis of this endpoint and therefore neither will be considered an intercurrent event.

Supplementary estimands for the two co-primary endpoints will use the same population and strategies for intercurrent events of treatment discontinuation, changes in background medication/starting a prohibited medication, interruptions of 2 or more consecutive doses of IP and COVID-19 pandemic related intercurrent events as for the primary estimand. Within the first supplementary estimand participants experiencing surgery or receiving a course of systemic CS for CRSwNP / ECRS will be assigned the worst possible score. Within the second supplementary estimand participants experiencing surgery will be assigned the participant's own worst observed score prior to the surgery event, the intercurrent event of course of systemic CS for CRSwNP / ECRS will be handled using a treatment policy strategy as in the primary estimand.

## 1.2. Study Design

Overview of Study Design and Key Features	
 
Keep current treatment throughout the study
 
Mepolizumab 100mg SC 13 doses, once every 4 weeks Week 0, 4, 8, 12, 16, 20, 24, 28, 32, 36, 40, 44, 48 (Visit 2, 3, 4, 5, 6, 7, 8, 9, 10, 11, 12, 13, 14)
 
Matching Placebo
 
N=80 per arm (total 160pts)
 
Double-blind treatment period
 
Week -4 Screening Visit 1      Week 0 Randomization (First Dose) Visit 2      Week 48 (Last Dose) Visit 14      Week 52 Primary Efficacy Endpoint Visit 15
	
Design Features
 
 
This is a randomised, double-blind, placebo-controlled, parallel group, multicentre Phase III study designed to assess the clinical efficacy and safety of 100 mg SC Mepolizumab treatment in adults with CRSwNP / ECRS.
 
The study will include a 4-week run-in period followed by randomisation to a 52-week treatment period as a double-blind, placebo-controlled phase. Throughout the entire study period (run-in + treatment period), participants will be on the SoC for CRSwNP / ECRS.
 
A participant is considered to have completed study treatment if he/she receives study treatment at Week 48 (Visit 14).
 
A participant is considered to have completed the study if he/she has completed all phases of the study including the last visit (Visit 15 / Week 52).
 
Initiation or changes in the background SoC dosing regimen are not permitted from screening to end of the study. Participants are expected, if possible, to continue with these treatments with no interruption nor alteration throughout the study duration.
 
A participant may discontinue from study treatment at any time at his/her own request, or at the discretion of the investigator. Participants who discontinue from study treatment prematurely (for any reason) should, where possible, continue to be followed-up as per protocol until the completion of the Week 52 Visit assessments.
 
Participants that discontinue from study treatment should return to clinic 4 weeks after the last dose for an Investigational Product (IP) Discontinuation Visit. Participants that withdraw from the study should return to clinic 4 weeks after the previous visit for an Early Withdrawal Visit.
 
Participants are permitted nasal surgery during the study without discontinuation from study treatment. The participant's nasal polyps surgical status will be tracked for the duration of the study. Following discontinuation of study treatment, as a minimum, participants will be contacted by telephone to enquire regarding any safety assessments and any nasal polyps surgery events (received a nasal polyps surgical procedure or entry into a waiting list for nasal polyps surgery).
 
For the purpose of this study, nasal polyps surgery is defined as any procedure involving instruments with resulting incision (cutting open) and removal of the polyp tissue from the nasal cavity (polypectomy / functional endoscopic sinus surgery [FESS]). Any procedure involving instrumentation in the nasal cavity resulting in dilatation of the nasal passage such as balloon sinuplasty, insertion
 


Overview of Study Design and Key Features	
	of coated stents or direct injection of steroids or other medication without any removal of nasal polyps tissue does not fulfil this criterion.
Study Treatment	
 
The treatment period will consist of thirteen doses of mepolizumab or matched placebo, delivered by a pre-filled safety syringe device (SSD) subcutaneous injection every 4 weeks for 52 weeks in addition to SoC therapy. The last dose of interventional product is to be administered at Week 48 (Visit 14).
 
For non-Japanese participants, study treatment must be administered by a healthcare professional (HCP) until week 52 (last dose at Week 48).
 
Japanese participants who are willing can self-administer study treatment under observation of the principal investigator or delegate from Week 32 onwards. Before allowing the self-administration, the principal investigator or delegate must assess the participant's knowledge/technique and document that they are competent to undertake self-administration. All self-administered injections will be assessed for success based on direct observation.
 
No dose modifications or dose reductions are permitted within the study protocol.
 
Participants meeting a treatment discontinuation criteria (which include pregnancy, liver stopping criteria or ECG stopping criteria as defined in Protocol Section 7.1.2) must have study treatment discontinued. Restart, re-challenge or resumption of study treatment following a stopping criteria being met is not permitted.
 

Study Treatment Assignment	
 
Approximately 160 participants to be randomised in a 1:1 ratio to mepolizumab or placebo treatment in accordance with the randomisation schedule (approximately 80 participants per arm).
 
The randomisation schedule will be generated using the GSK validated randomisation software RandAll NG. Eligible participants will be assigned to study treatment randomly using RAMOS NG, an Interactive Web Response System (IWRs).
 
The study will be randomised separately for each country and the randomisation will be stratified by background intranasal corticosteroids (INCS) use. Equal numbers of participants will be allocated to each treatment.
 

Interim Analysis	
 
No interim analysis of data is planned for this study.
 

[figure not shown]

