3. Parasitic screening is only required in countries with high-risk or for participants who have visited high-risk countries in the past 6 months. Sites should use local laboratories
4. A CT scan should be performed anytime during the run-in period up to a week prior randomisation. A second CT scan should be performed at V15 or IP discontinuation/Early Withdrawal visit (up to 14 days prior to the nominal study visit)
5. Urine Pregnancy test results to be assessed at all visits and prior to CT scan at Screening, V15 or IP discontinuation/Early Withdrawal Visit. If a urine test cannot be confirmed as negative (e.g., an ambiguous result), a serum pregnancy test is required.
6. eDiary completion by participants will be daily every morning between Screening Visit and Visit 15 (or IP discontinuation/Early Withdrawal Visit)
7. Genetics informed consent to be obtained any time prior sampling, Genetics sampling to be performed anytime while on treatment (Genetics sampling not applicable for participants in China)
8. Performed using eDiary device
9. All questionnaires will be performed before any other assessments on each particular visit, VAS scores (if not already completed at home), SNOT-22, (ACQ-5), SF-36 and WPAI. ACQ-5 should only be performed in Asthmatic participants. Order of questionnaires will be detailed in the Study Reference Manual.
10. SF-36 and WPAI will be performed at visits Baseline, week 4, week 24 and week 52 (or IP discontinuation/Early Withdrawal Visit) only
11. For endoscopic NP scores performed at V1, 3, 4, 6, 8, 10, 12, 14, 15 (or IP discontinuation/Early Withdrawal Visit), the nasal endoscopy assessment may be performed up to 3 days prior to the day of dosing but must not exceed the protocol defined windows of ±7 days from the nominal study visit. For V2, the endoscopic NP score cannot be performed earlier than V2 but must be performed at V2 upon completion of all screening procedures and prior to administration of IP.

12. For asthmatic participants only. An asthma exacerbation is defined as worsening of asthma requiring systemic corticosteroids (i.v. or oral steroid) for at least 3 days or a single IM CS dose and/or emergency department visit, or hospitalisation

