5.3. Randomisation Criteria

Those participants who meet the randomisation criteria below will be randomised into the study until the target of approximately 160 randomised participants is reached.

Participants will be randomised in a 1:1 ratio into one of two treatment groups, receiving a total of thirteen doses (one every four weeks):

- Group 1: 100 mg SC of mepolizumab on top of SoC
- Group 2: Placebo SC on top of SoC

[figure not shown]
The study will be randomised separately for each country and the randomisation will be stratified by background INCS use. Equal numbers of participants will be allocated to each treatment.

In rare instances and if following consultation with the Medical Monitor a participant can be rescreened. Rescreened participants are required to sign a new ICF.

At the end of the run-in period, study participants must fulfil the following additional criteria in order to be randomised to study treatment:

1. Confirmation of CRSwNP / ECRS with a JESREC Score $\geq 11^*$ [Tokunaga, 2015] using values measured between Visit 1 and 2 (central laboratory blood eosinophilic count, CT scan, nasal endoscopy as assessed by central laboratory).

CCI - This section contained Clinical Outcome Assessment data collection questionnaires or indices, which are protected by third party copyright laws and therefore have been excluded.

2. Confirmation of at least moderate CRSwNP / ECRS for participants with peripheral blood eosinophil count taken in the 12 months prior to Visit 0 OR through a blood sample taken between Visit 0 and Visit 1 of over 2% to 5% must have documented co-morbid disease of bronchial asthma, aspirin intolerance, or nonsteroidal anti-inflammatory drug intolerance. Participants with peripheral blood eosinophil count over 5% in the 12 months prior to Visit 0 OR through a blood sample taken between Visit 0 and Visit 1 do not require the presence of fore mentioned co-morbid diseases, and if the participant meets CT shadow: ethmoid \geq maxillary.
3. Endoscopic bilateral NP score of at least 5 out of a maximum score of 8 (with a minimum score of 2 in each nasal cavity) taken at Visit 1 as assessed at central laboratory
4. Mean nasal obstruction VAS > 5 over the last 7 days preceding Visit 2 (excluding Visit 2) (from eDiary)
5. eDiary compliance for VAS (at least 4 out of the last 7 days preceding Visit 2, (excluding Visit 2)).

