## 2. STATISTICAL HYPOTHESES

The study is designed to test the superiority of mepolizumab 100mg SC vs. placebo in both co-primary efficacy endpoints of total endoscopic nasal polyp score at Week 52 and nasal obstruction VAS score during the 4 weeks prior to Week 52. Each co-primary endpoint will be tested at the two-sided 5% alpha level (one-sided 2.5%) and both tests are required to be significant to achieve the primary objective of the study.

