#### 4.1.2. Baseline Definition

##### 4.1.2.1. Visit-Based Endpoints

For all visit-based endpoints, including the co-primary endpoint of endoscopic NP score, Baseline will be defined as the latest non-missing measurement collected prior to the first dose of study treatment. This will generally be from the Day 1 (Visit 2) assessment but may be from an unscheduled assessment. Where time is collected, an assessment is valid for use as Baseline if the date and time is prior to or the same as the date and time of first dose. Where time is not collected, an assessment is valid for use as Baseline if the date of assessment is on or before the date of first dose.

Unless otherwise stated, if baseline data is missing no derivation will be performed and baseline will be set to missing.

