- e) Course of systemic CS for CRSwNP / ECRS – to be handled using a treatment policy strategy. Data collected following a course of systemic CS for CRSwNP / ECRS will be included in the analysis where systemic CS will be considered as SoC treatment.
- f) Interruption to investigational product of 2 or more consecutive doses – to be handled using a treatment policy. These events will be recorded as protocol deviations and participants are expected to continue investigational product per-protocol after interruption. Data collected will be included in the analysis regardless of IP interruption.

This analysis will utilise the change from baseline in each of the co-primary endpoints where data for participants with surgery (prior to visit) are based on the worst possible score from the day after surgery onwards.

There are two expected sources of missing data namely, participants who withdrew early from study and participants who experienced an intercurrent event due to COVID-19 pandemic related restrictions. For the primary analysis, all missing data is assumed to be missing at random (MAR).

Analysis will be carried out using a mixed model repeated measures analysis with covariates of treatment group, baseline value, log of baseline blood eosinophil count, background INCS use (actual strata based on information related to INCS use recorded on eCRF), country and time point, plus interaction terms for time point by baseline value and time point by treatment group. Models will be checked for issues with convergence.

An unstructured covariance structure for the R matrix will be used by specifying 'type=UN' on the REPEATED line. The Kenward and Roger method for approximating the denominator degrees of freedom and correcting for bias in the estimated variance-covariance of the fixed effects will be used. The estimated means for each treatment group will be calculated from the model using the observed marginal distributions of the sample covariates (OM option in LSMEANS statement). Model-estimates of the absolute mean and mean change from baseline will be presented with corresponding standard errors for each treatment group by visit. Estimated treatment differences (Mepolizumab - Placebo) with corresponding 95% CIs and p-values will also be presented.

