## 5. SAMPLE SIZE DETERMINATION

The sample size is based on the co-primary efficacy endpoints of total endoscopic nasal polyp score at Week 52 and nasal obstruction VAS score during the 4 weeks prior to Week 52.

The sample size of 160 participants randomised in a 1:1 ratio to each treatment arm provides at least 90% power to demonstrate a statistically significant result for both co-primary endpoints using a mixed model repeated measures (MMRM) analysis model.

Estimates of residual standard deviation (SD) of 1.82 for total endoscopic nasal polyp score at Week 52 and 3.25 for nasal obstruction VAS score during the 4 weeks prior to Week 52 are taken from a post-hoc MMRM analysis of observed data from study 205687 (SYNAPSE) which assumed a “missing at random” (MAR) assumption for missing data.

With the above assumptions and a sample size of 160 randomized subjects (80 per arm), it is estimated that the null hypothesis will be rejected at the two-sided 5% level of significance for total endoscopic nasal polyp score if the observed difference between treatments is at least 0.57 units and for nasal obstruction VAS score if the observed difference between treatments is at least 1.01.

For total endoscopic nasal polyp score, if the true difference between treatments is 1.00 units, then the study has a probability of 93.2% of observing a difference in total endoscopic nasal polyp score between treatments of at least 0.57 units and therefore 93.2% power for declaring significance on this endpoint. The estimated improvement observed in total endoscopic nasal polyp score for mepolizumab 100 mg SC compared to placebo within study 205687 (SYNAPSE) was 0.99 units (95% CI: 0.61 to 1.36).

For nasal obstruction VAS score, if the true difference between treatments is 2.00, then the study has a probability of 97.2% of observing a difference in nasal obstruction VAS score between treatments of at least 1.01 units and therefore a 97.2% power for declaring significance on this endpoint. The measured improvement observed in nasal obstruction VAS score for mepolizumab 100 mg SC compared to placebo within study 205687 (SYNAPSE) was 1.97 units (95% CI: 1.31 to 2.63).

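### The Visit 1 centrally read NP score is collected but not used in the NP co-primary model; adding it is a cheap, small gain in precision, not the correction of an error

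*SAP*

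**What the plan says.** SAP 1.2 sets out the design: "The study will include a 4-week run-in period followed by randomisation to a 52-week treatment period". NP scores are read at both ends of that run-in.

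Protocol 5.3, randomisation criterion 3, requires an NP score of at least 5 (at least 2 per side) "taken at Visit 1 as assessed at central laboratory". Protocol 5 allows no waivers of entry criteria, so a participant randomised per protocol has this read.

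A second endoscopy is done at the baseline visit. Protocol 1.3, footnote 11: "For V2, the endoscopic NP score cannot be performed earlier than V2 but must be performed at V2", before dosing. Protocol 8.2.1 makes the central reading final for both eligibility and analysis, so both reads come from the same source on the same 0–8 scale.

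Only one of them enters the analysis. SAP 4.1.2.1: "Baseline will be defined as the latest non-missing measurement collected prior to the first dose of study treatment", generally Visit 2. SAP 4.2.2 lists "covariates of treatment group, baseline value, log of baseline blood eosinophil count, background INCS use", then country, time point, and the interactions of time point with baseline and with treatment. Protocol 9.4.1 has the same model. No readable section uses the Visit 1 read as a covariate. For comparison, the VAS baseline is already a mean of up to seven diary days (SAP 4.1.2.2).

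**The concern.** One NP read is an integer score with reading error, so adjusting for it captures a participant's underlying polyp burden only in part. A second pre-randomisation read of the same quantity can recover some of the rest. Adjusting for it leaves the estimand unchanged and does not bias the comparison.

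The point bears on the NP score because success requires both co-primaries (SAP 2) and the NP score has the lower stated power. What is at stake is a little precision, not validity.

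**Working it through.** **Inputs from SAP 5.** "160 participants randomised in a 1:1 ratio to each treatment arm", that is, 80 per arm; two-sided 5%; NP difference 1.00 with SD 1.82; VAS difference 2.00 with SD 3.25.

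**1. Reproduce the plan.** Noncentral t, 158 df, noncentrality = difference / (SD × √(2/80)):
- NP: power 93.24% (stated 93.2%), critical difference 0.568 (stated 0.57).
- VAS: power 97.18% (stated 97.2%), critical difference 1.015 (stated 1.01).
- Joint power at zero correlation: 0.9324 × 0.9718 = 90.6%. Lower bound whatever the dependence: 0.9324 + 0.9718 − 1 = 90.4%.

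All 50 cells of Protocol Table 1 reproduce to 0.1 point.

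**2. Gain by formula.** Two quantities are assumed, because the documents give neither: r, the correlation of the Visit 1 and Visit 2 reads, and ρ, the correlation of one read with the Week 52 score. Treating the reads as parallel measures, and taking SD 1.82 as already adjusted for one read,

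variance ratio = [1 − 2ρ²/(1 + r)] / (1 − ρ²).

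Middle case, ρ = 0.4 and r = 0.7: (1 − 0.32/1.7) / 0.84 = 0.8118 / 0.84 = 0.966. SD becomes 1.82 × √0.966 = 1.79. With 157 df, NP power is 94.0% and joint power 0.940 × 0.9718 = 91.3%. The equivalent sample is 160 / 0.966 ≈ 166, about 6 more participants.

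| ρ | NP power, r = 0.9 | NP power, r = 0.5 |
|---|---|---|
| 0.2 | 93.3% | 93.5% |
| 0.3 | 93.4% | 94.0% |
| 0.4 | 93.5% | 94.6% |
| 0.5 | 93.6% | 95.6% |
| 0.6 | 93.9% | 96.9% |

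The bottom rows are optimistic here. The entry rule confines Visit 1 reads to 5–8, Week 52 is a year away, and surgery is scored as the worst value. Simulated integer reads with the entry cut gave ρ of only 0.20–0.37.

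**3. Gain by simulation, and what drives it.** Assumed: true level SD 1.0–1.3, read error SD 0.5–0.9, integer reads, Visit 1 read ≥ 5, Week 52 residual SD 1.7. The slope is the share of a baseline difference in true level that persists to Week 52.

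| Slope | Surgery scoring | Variance reduction | Joint power |
|---|---|---|---|
| 1.0 | none | about 3–4.5% | 91.2–91.6% |
| 0.7 | none | 1.5–2.6% | 90.9–91.2% |
| 0.5 | none | 0.8–1.4% | 90.8–90.9% |
| 1.0 | 15% scored 8 at random | about 1.6–2.7% | about 91.0–91.2% |
| 0.5 | 15% scored 8 at random | 0.4–0.7% | about 90.7–90.8% |

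Slope and surgery share are also assumptions. If surgery tracks baseline severity, the loss in the last two rows would be smaller.

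**4. Cost.** The figures above charge one degree of freedom. Estimating an extra covariate also costs about 1/157 = 0.6% of variance through chance imbalance, so it pays only if its partial correlation with the Week 52 score exceeds √(1/157) ≈ 0.08. The last row of the table is therefore close to no net gain.

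**The case against.** The strongest reply is that nothing is wrong. Adjusting for the latest pre-dose value, with its time-point interaction, is valid and conventional, and the plan already meets its 90% target. That stands in full.

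The 90.6% figure also assumes uncorrelated endpoints. The shared surgery rule favours positive correlation; joint power is then about 91.4% at correlation 0.5 and 92.0% at 0.7 with no change to the model. That stands too, and it makes the gain less needed.

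A main effect for Visit 1 would impose one coefficient on eight post-baseline endoscopy visits (Weeks 4 to 52), whereas the calculations concern Week 52 alone. An interaction is needed, which means eight parameters in an unstructured model; SAP 4.1.3 already foresees convergence trouble. This shapes the fix rather than defeating it.

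A reader might infer three stronger things that the documents do not support:
- *That every randomised participant has two reads.* If the Visit 2 read is missing, SAP 4.1.2.1 makes an earlier value the baseline, which may be Visit 1 itself.
- *That the power claim is unsafe and this covariate would protect it.* At SD 1.86, Protocol Table 1 gives 92.2%, so joint power at zero correlation is 0.922 × 0.972 = 89.6%. Offsetting that step needs a variance cut of 1 − (1.82/1.86)² = 4.3%, above the plausible 1–3%.
- *That the same should be done for VAS.* Its baseline already averages up to seven days, diary compliance is required only for those days (Protocol 5.3, criterion 5), a cold may prolong the run-in, and stated power is 97.2%.

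**Conclusion.** The point holds as a cheap improvement. The Visit 1 central read exists for participants randomised per protocol, is measured before randomisation on the same scale, and is not used. Under assumed ranges, Week 52 residual variance falls by about 0.5–5%, most plausibly 1–3%, and joint power at zero correlation rises from 90.6% to about 90.7–91.7%. The upper end needs baseline differences to persist almost fully for a year with little dilution from surgery scoring. If Week 52 depends only weakly on baseline, the net gain is close to nil. The documents give neither the read-to-read nor the baseline-to-Week 52 correlation, so the range cannot be narrowed from them. Leaving the model as it is would not be a defect.

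**What to change.** Before unblinding, amend SAP 4.2.2 for the NP score model only:
- Add the Visit 1 centrally read NP score and its interaction with time point, matching the existing baseline terms.
- Keep change from the latest pre-dose value as the endpoint.
- If the Visit 2 read is missing, use the Visit 1 value for both terms.
- If the model does not converge, drop the Visit 1 interaction first.
- Add a row to SAP Table 3 (Section 4.13), since Protocol 9.4.1 specifies the current covariates.

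The cost is SAP wording and up to eight model parameters; no new data or visits. No change to the VAS model is recommended.
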